2.3 Effectiveness

Results of prostate mapping biopsies will be used to assess lesion control achieved by the treatment.

Focal MR-Guided Focused Ultrasound Surgery of Intermediate risk, Localized Prostate Lesions

Post-treatment PSA, non-perfused volume (NPV), FACT-P (Version 4), ICIQ-SF, IPSS, IIEF-15 and SF12 questionnaire results through Month 24 visit will be summarized as secondary measures of effectiveness.

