4 INVESTIGATION PLAN

4.1 Study Design

This is a multi-center, prospective, single arm study to evaluate MRgFUS treatment of intermediate risk, organ-confined prostate lesions. All subjects will be treated and then followed up clinically for up to 24 months to evaluate any procedure or device related

**Focal MR-Guided Focused Ultrasound Surgery
of Intermediate risk, Localized Prostate Lesions**

adverse events as well as to assess efficacy endpoints of the study. Additional data related to quality of life of treated subjects will also be collected.

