6.2 Data Analysis

6.2.1 510(k) Analysis

This is a clinical study involving a minimum of 100 to a maximum of 103 subjects. Descriptive analyses of safety and effectiveness data will be used to summarize results for a 510(k) submission for commercial clearance. Safety and effectiveness data will address both results of biopsy as well as functional analysis.

Primary effectiveness analyses will be based on the 6-month biopsy results. Proportions of treated patients reporting a negative biopsy and/or MRI verification of index lesion ablation at 6-months.

Descriptive summaries will be presented for: PSA testing, NRS, FACT-P (v4), IPSS, and SF-12 questionnaires and percentage of non-perfused volume (NPV).

Baseline assessment of erectile dysfunction and incontinence will be captured as per the incontinence/ED questionnaires and they will be followed also using the same questionnaires. Any

Focal MR-Guided Focused Ultrasound Surgery of Intermediate risk, Localized Prostate Lesions

worsening of the baseline condition to a worsened CTCAE grade will be captured as an adverse event and will be graded on CTCAE Version 4.0 published May 28, 2009 (v.4.03:June 14, 2010) and will be reviewed by the Data Safety Monitoring Board.

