7.1.7 Risks associated with the ExAblate MRgFUS treatment and/or biopsy mapping

- While the goal of the ExAblate treatment is to completely ablate the prostate tissue lesion(s), there is a risk that abnormal tissue may still exist for varying reasons including failed biopsy detection at screening and/or incomplete ablation of the entire lesion.
- Pain or discomfort requiring oral analgesia is expected to occur in almost all patients after treatment.
- Severe pain in the treatment areas (pelvis, rectum or scrotum area) for which patients return to the physician/hospital is reported in 1.4-3% of the treatments. Pain symptoms will be specified for location and recorded in the CRFs for occurrence and duration; severity will be measured by NRS score during post-treatment follow-up.
- Incontinence rates following resolution of immediate dysuria are <2%. In patients undergoing primary HIFU treatment. In the treatment performed with the ExAblate MRgFUS device, the urethral sphincters are preserved by marking them as LEDR's, thus avoiding therapeutic dose accumulation at these structures. The ability to customize the energy to the specific case and the real-time monitoring and control of the applied energy, associated with the MRI which provides high resolution visualization of the anatomical structures, significantly reduces the risk of urinary sphincters injury. Thus, we expect even lower rates of incontinence after ExAblate treatments.
- Erectile dysfunction in previously potent men is reported to range between 40 and 50% in ultrasound-guided HIFU treatments. In ExAblate MRgFUS treatments, the NVB's are clearly visualized and can be protected if needed by marking them as LEDR's. We expect therefore, that in potent patients that have no evidence for cancer adjacent to the NVB's – post-treatment impotence rate will not exceed 10%.
- Retrograde ejaculation - since the treatment includes the orifices of the seminal vesicles in the urethra, retrograde ejaculation may be permanent in 3% of the patients; occurrence, duration and treatment will be recorded in the CRF's.
- Perineal hematoma development as a result of treatment is very low. The probe is inserted, manipulated extracted by authorized experienced Urologists. No sharp edges are in contact with the rectum At the end of the ExAblate procedure, a contrast (Gadolinium) enhanced MR imaging is performed to assess the blood flow within the treated area and neighboring tissue.

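### Section 6.2.1 counts erectile and continence harm by worsening of CTCAE grade and plans no rate in men potent or continent at baseline, the group to which the erectile figures in 7.1.7 apply; it also omits IIEF-15 and ICIQ-SF from its summaries

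*Combined protocol and SAP*

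**What the plan says.** - **Objective.** Section 2.1 lists the risk of treatment-related incontinence and impotence among the safety questions.
- **Event rule.** Section 6.2.1 has erectile dysfunction (ED) and incontinence assessed at baseline and followed with the same questionnaires. It then states that any "worsening of the baseline condition to a worsened CTCAE grade will be captured as an adverse event", graded on CTCAE version 4 and reviewed by the Data Safety Monitoring Board. No denominator is given. Section 2.2 sets an overall safety window to 24 months, but no visit is named at which an ED or incontinence rate is to be read.
- **Summaries.** Section 6.2.1: "Descriptive summaries will be presented for: PSA testing, NRS, FACT-P (v4), IPSS, and SF-12 questionnaires", plus non-perfused volume. IIEF-15 and ICIQ-SF are not in that list. Section 2.3 says that "ICIQ-SF, IPSS, IIEF-15 and SF12 questionnaire results through Month 24 visit will be summarized as secondary measures of effectiveness", and Section 2.1 plans change from baseline to 24 months for the same instruments.
- **Reference figures.** Section 7.1.7 expects that "in potent patients that have no evidence for cancer adjacent to the NVB's – post-treatment impotence rate will not exceed 10" percent. It cites 40-50% ED in previously potent men after ultrasound-guided HIFU, and incontinence below 2% after primary HIFU.
- **Population and design.** The criteria in Sections 3.2 and 3.3 set no threshold for erectile function or continence. The study is single arm, with "a minimum of 100 to a maximum of 103 subjects", and the 510(k) analysis is descriptive.

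**The concern.** Sparing erectile function and continence is the stated attraction of focal treatment (Sections 1.2 and 1.3). With no control arm, outside figures are the only yardstick, and the erectile ones are conditional on potency before treatment. The grade-worsening count is not. It takes in men aged 50 or older who may already be impotent, and it counts a one-grade step whether or not potency was lost. Followed as written, Section 6.2.1 yields a number that does not estimate the quantity in Section 7.1.7. Because the denominator is open, it could also be settled after the results are known. The two questionnaires that measure these harms are the ones missing from the 6.2.1 list.

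**Working it through.** **Inputs from the documents.** Treated men: 100 to 103 (6.2.1). Expected impotence: at most 10%, in potent men without cancer adjacent to the nerve bundles (7.1.7). Reference incontinence: below 2% (7.1.7).

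**Inputs assumed, because the documents give none.** f = share of men potent at baseline, taken from 50% to 90%; p = event rate in potent men; q = rate of grade worsening in men not potent at baseline.

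**Reproducing the plan's figure.** This is not possible. The 10% is stated without inputs, and the sample size has no alpha, power or precision target.

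**1. What a mixed rate estimates.** If all treated men were the denominator:

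mixed rate = f × p + (1 − f) × q

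**2. Case q = 0 (no man impotent at baseline worsens by a grade).** Then p = mixed rate / f. For 10 events in 100 treated men:

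| Potent at baseline | Rate in potent men |
|---|---|
| 50 | 10/50 = 20.0% |
| 60 | 10/60 = 16.7% |
| 70 | 10/70 = 14.3% |
| 80 | 10/80 = 12.5% |

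The gap from 10% is 2.5 to 10 percentage points.

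**3. Case q > 0.** Take f = 50% and p = 10%:

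- q = 0: 0.5 × 10% + 0.5 × 0% = 5.0%
- q = 5%: 5.0% + 2.5% = 7.5%
- q = 10%: 5.0% + 5.0% = 10.0%
- q = 20%: 5.0% + 10.0% = 15.0%

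So the mixed rate can be below, equal to or above the rate in potent men. When q = p it equals p at any f.

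**4. Could the denominator change the reading?** Suppose the true rate in potent men is 20%, twice the expectation, with q = 0 and 100 treated men. Exact binomial probabilities of observing at most 10%:

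| Potent men | All treated as denominator (10 or fewer events) | Potent men as denominator |
|---|---|---|
| 50 | 58% | 5% (5 or fewer) |
| 70 | 15% | 2% (7 or fewer) |
| 90 | 2% | 1% (9 or fewer) |

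**5. Precision with the at-risk denominator.** Exact (Clopper-Pearson) 95% intervals: 10/50 = 20%, 10.0-33.7%; 10/80 = 12.5%, 6.2-21.8%; 5/50 = 10%, 3.3-21.8%; 7/70 = 10%, 4.1-19.5%. For comparison, 10/100 = 10%, 4.9-17.6%.

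**6. Continence.** If 80% to 95% of men are continent at baseline (assumed) and only they can have the event, 2% becomes 2% × 0.80 = 1.6% to 2% × 0.95 = 1.9%. The effect is small.

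**The case against.** A reader might infer several stronger things that the documents do not support.

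- **That these harms are recorded only through CTCAE grade.** They are not. Section 6.2.1 follows both conditions by questionnaire and promises functional analysis in general terms, and Sections 2.1 and 2.3 plan change from baseline and summaries. What holds is narrower: grade worsening is the only event definition.
- **That all treated men are the chosen denominator, so the rate is diluted in the device's favour.** The text names no denominator. The rule covers men who start with a condition and get worse, so they can contribute events, and step 3 shows that the direction is not fixed.
- **That the study would pass a 10% test it should fail.** The 10% is an expectation in the risk section, not an endpoint or performance goal, and the analysis is descriptive: "Descriptive analyses of safety and effectiveness data will be used to summarize results for a 510(k) submission for commercial clearance". No section plans a comparison with the 10% or the 40-50%.
- **That function results will be left out of the submission.** The missing instruments are a conflict between two lists. They do not show an intention to leave results out, and IPSS and FACT-P remain in the 6.2.1 list.

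Two practical limits also stand. Complete 24-month rates cannot be in a 510(k) filed after the last 12-month visit (2.1). No section lists tumor adjacency to the nerve bundles as a recorded item.

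The objection leaves the main gap in place. Whichever denominator is used for the grade-worsening count, no rate is planned in men who had function to lose, and that is the population of both erectile figures in 7.1.7.

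**Conclusion.** The concern holds as a wrong-quantity and consistency problem that should be corrected. It does not show bias in a known direction. Section 6.2.1 defines neither potency nor continence, sets no denominator or time point for new ED or incontinence, plans no at-risk rate, and disagrees with 2.1 and 2.3 on the instruments summarized.

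The 12.5-20.0% range for a mixed rate of 10% rests on three assumptions: 50 to 80 potent men per 100, all treated men as denominator, and no grade worsening in men impotent at baseline. If the third fails, the gap shrinks, vanishes or reverses. The material issue is erectile function. For continence the gap is mainly one of definition, provided most men enter continent.

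**What to change.** In Section 6.2.1:

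1. Define baseline potency by a pre-stated IIEF-15 criterion and baseline continence by ICIQ-SF. The Section 5 schedule labels the former IIEF-15 (SHIM), so the criterion should name the score it uses.
2. Report new ED among men potent at baseline and new incontinence among men continent at baseline, with the number at risk and exact 95% intervals. Do this at 6 and 12 months for the 510(k) and at 24 months in the final analysis.
3. Keep the all-treated CTCAE table beside these rates, with its denominator stated.
4. Add IIEF-15 and ICIQ-SF change from baseline to the list of descriptive summaries, so that 6.2.1 agrees with 2.3 and 2.1.
5. Show the subgroup without cancer adjacent to the nerve bundles, the exact population of the 10% expectation, only if adjacency can be read from the baseline MRI and biopsy records.

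**Cost.** Wording and a few tables. Both questionnaires are already scheduled at screening, before treatment, and at 3, 6, 9, 12, 18 and 24 months, so no visits are added. The statistical price is a smaller denominator and a wider interval, for example 10/50 = 20% with a 95% interval of 10.0-33.7%. Item 5 may need extra abstraction from source records.

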6.2.2 Final Analysis

Final safety and effectiveness analyses will be presented to the FDA per 510K submission requirements.

7 RISK ANALYSIS

Worldwide, over 5000 treatments have been performed to date with the MR guided FUS ExAblate 2000 device. Risk analysis for InSightec ExAblate systems/clinical investigations has been conducted as part of previously approved FDA IDE submissions (G930140, G990151, G990184, G990201, G000203, G010225, G020001, G020182, G050177, and G060023, G070022, G080009, G080206, G100127, G100169, G120017, G120246, G140018, G140082, P040003 and subsequent supplements, P110039, and P150038). This data has been re-examined by the study sponsor and it has been concluded that this risk analysis is applicable to the proposed clinical investigation. The key consideration here is the fact that this proposed study has the same purpose as the previous ones, namely to coagulate soft tissue within the body by means of ExAblate. The original risks and additional risks, new and unique to this study are discussed below.

Potential risks described below will be explained to subject in the informed consent process.

7.1 Potential risks

7.1.1 Risk of Transperineal Mapping Biopsy

Transperineal biopsy is associated with^{7,8}:

- ~10% risk of urinary retention after biopsy in patients with large prostates (>60 mL)
- 20-42% of hematuria
- 13-50% of hematospermia
- 31% of pain (18% requiring analgesia after procedure)
- 6:1000 -1.2% risk for sepsis

⁷ Webb JA, Shanmuganthan K, McLean A. Complications of ultrasound guided transperineal biopsy. A prospective study. Br J Urol. 1993; 72: 775-7

⁸ Miller J, Perumalla C, Heap G. Complications of transrectal versus transperineal prostate biopsy. ANZ J Surg. 2005; 75:48-50.

Focal MR-Guided Focused Ultrasound Surgery of Intermediate risk, Localized Prostate Lesions

7.1.2 Risk related with Transrectal Mapping Biopsy

Transperineal biopsy is associated with

- Urinary retention requiring catheterization for bladder drainage is seen in ~1%
- Discomfort and pain in the rectal area in > 80% of the patients
- Hematuria occurs in about 66% of the patients and may persist for 3-7 days in about 50% of the patients
- Hematospermia is reported in about 1-2% of the patients
- Rectal bleeding occurs roughly in 9%-27% of the patients
- Infection (most frequently – UTI) requiring hospitalization occurs in about 0.7% of the patients undergoing prostate biopsy

7.1.3 Risk of MR Imaging

- Study subject may find MR unit claustrophobic and request to leave the study despite pre-procedure sedation.
- MRI has no known deleterious biological effects in patients with no contraindications. The incidence of claustrophobia during MRI examinations is approximately 10-15%, although it is expected to be less frequent in the study population due to the use of sedation.
- Gadolinium DTPA (Magnevist/Omniscan) is an intravenously injectable contrast medium for MRI. The package insert notes that there are no known contraindications. Precautions should be exercised for patients with a history of grand mal seizures, severely impaired renal function or hemolytic anemia. The very unlikely possibility of a reaction, including anaphylactic or cardiovascular reactions, should be considered especially for patients with a known sensitivity to Gd or history of asthma. Adverse reactions include: headache (incidence 8.7%), localized pain, vomiting, paresthesia, and dizziness and localized warmth (incidence less than 2%). Additional adverse effects listed on the package insert occur with an incidence of less than 1%.
- Nephrogenic Systemic Fibrosis (NSF) or Nephrogenic Fibrosing Dermopathy (NFD), kidney disorders, may occur in patients with moderate to end-stage kidney disease after they have had a MRI scan with gadolinium-based contrast agent. NSF causes fibrosis of the skin and connective tissues throughout the body. Patients develop skin thickening that may prevent bending and extending joints, resulting in decreased mobility of joints. NSF usually starts in the lower extremities. Fibrosis can also develop in the diaphragm, muscles in the thigh and lower abdomen, and lung vessels.

7.1.4 Risks related to the use of a urinary catheter:

- Local discomfort and/or pain that might last up 1 or 2 days after catheter removal

Focal MR-Guided Focused Ultrasound Surgery of Intermediate risk, Localized Prostate Lesions

- Partial or complete urinary retention is expected in all patients for the first post-treatment 48 hours. It may last however longer or occur after successful voiding (in 1-9% of the patients).
- Urinary retention requiring surgical intervention may occur in 2% of the cases. Occurrence, severity, duration and management will be recorded in the CRF and AE form
- Urethral stricture requiring intermittent sound dilatation or bladder neck stricture requiring bladder neck incision is reported in 1-25%. (Usually rates are less with SPC than with Foley catheter.) The use of SPC and the ability to plan around structures, such as the bladder wall by using the editor function of the software (LEDR) expected to reduce the risk of bladder neck injury.
- Dysuria – immediate dysuria due to prostatic urethral sloughing occurs in all patients for a week following treatment, but dysuria may last even 6 weeks. Dysuria may be associated with urinary tract infection. Measurement will be by NRS score during post-treatment visits; duration and treatment will be recorded in the CRF.
- Perineal edema may occur in some patients and this usually resolves spontaneously and completely within 7 days.
- Urinary tract infection (UTI) is frequent (reported in 5-48%) due to the prolonged catheterization and non-sterile handling. Patients and their supporting family members will be instructed to handle the catheter adequately, and patients will be under oral antibiotics until catheter extraction, but it should be expected that even then symptomatic UTI will occur. Occurrence of symptomatic UTI, symptoms, severity, duration and management will be recorded in the CRF and AE form.
- Occasionally, infection persists and leads to such complications as prostatitis, epididymitis, cystitis, pyelonephritis.⁹ Prostatitis (reported in less than 2%) and/or epididymo-orchitis (manifested as pain, swelling and tenderness in the scrotum) is reported in 5-7.5% of the patients who were fitted with a SPC (as opposed to 8.5% in patients with urethral catheter. occurrence, duration and treatment will be recorded in the CRF and AE form.

7.1.5 Risks Related to Anesthesia

7.1.5.1 Epidural anesthesia may involve the following risks:

- Low blood pressure, which is the reason the patient is routinely hydrated prior to the placement of either of these forms of anesthesia.

⁹ Kunin CM. Detection, prevention, and management of urinary tract infections. 3rd ed. Philadelphia: Lea and Febiger, 1979.

Focal MR-Guided Focused Ultrasound Surgery of Intermediate risk, Localized Prostate Lesions

- Postdural puncture headache occurs infrequently with these techniques. The risk is 1% with Epidural. This is believed to be due to a leak of Cerebrospinal fluid from the needle hole in the dura.
- Backache is an infrequent problem. It most likely is due to ligament strain due to profound muscle relaxation or surgical positioning.
- Other complications that can occur include, but are not limited to, infection, nerve damage (including paralysis, loss of bladder and bowel function, loss of sexual function), allergic reactions, seizures, cardiac arrest and death. Although the result of these is severe they occur very rarely.

7.1.5.2 General anesthesia may involve the following risks:

- Serious side effects of general anesthesia (GA) are uncommon in people who are relatively healthy when conducted by a certified Anesthesiologist with required resuscitation skills (as required in this study).

Estimated death rate 1:2,000,000-250,000 cases; and overall complication rate is <3%
- Aspiration - GA suppresses the normal throat reflexes that prevent aspiration, such as swallowing, coughing, or gagging. To help prevent aspiration, an endotracheal (ET) tube is inserted during general anesthesia. When an ET tube is in place, the lungs are protected so stomach contents cannot enter the lungs. Aspiration during anesthesia and surgery is very uncommon. To reduce this risk, patients are instructed not to eat or drink anything for 12 hours before anesthesia so that the stomach is empty, per local site standards.
- Changes in blood pressure or heart rate or rhythm
- Cardiac event, or stroke
- Damage to teeth and lips
- Swelling in the larynx
- Sore throat and/or hoarseness caused by injury or irritation of the larynx.
- Allergic reactions to medications are rare – potential allergies will be evaluated by the anesthetist before anesthesia.
- Nausea and vomiting after anesthesia – occur in less than 10% of the patients

7.1.6 Risks incidental to the treatment

- There is a potential risk to the patient of deep venous thrombosis from lying stationary for 3 to 4 hours. The risk to the patient from lying still for this treatment should be no greater than of lying still for any other reason. For treatments under this protocol,

Focal MR-Guided Focused Ultrasound Surgery of Intermediate risk, Localized Prostate Lesions

it will be the surgeon discretion to provide patients with compression stockings or wraps for the period of the treatment.

- There is a risk that the patient may experience a sore neck or discomfort from lying in the same position for a long time during the treatment.

7.1.7 Risks associated with the ExAblate MRgFUS treatment and/or biopsy mapping

- While the goal of the ExAblate treatment is to completely ablate the prostate tissue lesion(s), there is a risk that abnormal tissue may still exist for varying reasons including failed biopsy detection at screening and/or incomplete ablation of the entire lesion.
- Pain or discomfort requiring oral analgesia is expected to occur in almost all patients after treatment.
- Severe pain in the treatment areas (pelvis, rectum or scrotum area) for which patients return to the physician/hospital is reported in 1.4-3% of the treatments. Pain symptoms will be specified for location and recorded in the CRFs for occurrence and duration; severity will be measured by NRS score during post-treatment follow-up.
- Incontinence rates following resolution of immediate dysuria are <2%. In patients undergoing primary HIFU treatment. In the treatment performed with the ExAblate MRgFUS device, the urethral sphincters are preserved by marking them as LEDR's, thus avoiding therapeutic dose accumulation at these structures. The ability to customize the energy to the specific case and the real-time monitoring and control of the applied energy, associated with the MRI which provides high resolution visualization of the anatomical structures, significantly reduces the risk of urinary sphincters injury. Thus, we expect even lower rates of incontinence after ExAblate treatments.
- Erectile dysfunction in previously potent men is reported to range between 40 and 50% in ultrasound-guided HIFU treatments. In ExAblate MRgFUS treatments, the NVB's are clearly visualized and can be protected if needed by marking them as LEDR's. We expect therefore, that in potent patients that have no evidence for cancer adjacent to the NVB's – post-treatment impotence rate will not exceed 10%.
- Retrograde ejaculation - since the treatment includes the orifices of the seminal vesicles in the urethra, retrograde ejaculation may be permanent in 3% of the patients; occurrence, duration and treatment will be recorded in the CRF's.
- Perineal hematoma development as a result of treatment is very low. The probe is inserted, manipulated extracted by authorized experienced Urologists. No sharp edges are in contact with the rectum At the end of the ExAblate procedure, a contrast (Gadolinium) enhanced MR imaging is performed to assess the blood flow within the treated area and neighboring tissue.
- Unintended ablation of vulnerable structures outside the planned treatment volume due to improper targeting of the focal point At the start of treatment, the system includes a mandatory step that requires the operator to first check the alignment of

Focal MR-Guided Focused Ultrasound Surgery of Intermediate risk, Localized Prostate Lesions

the patient anatomy, the focal point of the transducer and the MR imaging system in all three axes. This procedure is done while the patient is in position for treatment. Then the operator has to mark the prostate capsule (to detect potential movements of the organ during the treatment), the desired treatment boundaries and the structures that should be preserved (i.e., rectum, sphincters, bladder wall, urethra, NVB). For each sonication delivered during treatment, the operator gets continuous feedback on the position of the treatment point superimposed on the anatomical image and can make geometrical and dose corrections where required. The system also includes an independent safety-monitoring loop that continuously compares the physical position of the transducer for any un-commanded motion in the system from any source. If such a move is detected, the system immediately stops the delivery of energy to the patient, and notifies the operator of the error. The rectal wall is especially protected by cooling the degassed water inside the balloon to 14°C.

- The protocol results in the necrosed tissue being left *in situ* to be naturally removed by the body. There is a potential risk to the patient from a reaction to the volume of treated tissue (fever or infection). This effect has been often observed in other technologies of tissue ablation such as Cryo-therapy or Radiofrequency ablation of other lesions but rarely seen in ExAblate MRgFUS ablation. Furthermore, since the treatment in this protocol is a focal treatment that will never exceed 35 cc this concern practically almost does not exist. Overall treatment volume should be up to 50% of the prostate gland for prostate volume <60cc, and up to 30cc should the entire prostate volume be larger than 60cc.
- A risk of damage to the rectal wall from either targeting a prostate area that is too close to the rectal wall or from problems in acoustic coupling between the balloon and the rectal wall or from unexpected high acoustic absorption at the rectal wall. Fistulae were reported in about 0.5% of the Ultrasound-guided HIFU patients. The system includes water cooling of the interface, planning aimed to protect the rectal wall; automatic warning to the user if an edited spot is too close to the rectal wall, and use of acoustic gel as a coupler between the balloon and the rectum. Based on animal trials and few initial feasibility studies, the rectal wall is adequately protected from thermal injury.
- There is a risk of patient motion during a sonication, or between sonications. This could cause a movement of the tumor relative to the planned treatment volume on the system, and in extreme cases could result in the treatment of a point outside the planned treatment volume. Motion tracking is being done by the operator using fiducials placed on the anatomic images and by integrated 3D tracker inside the transducer. The use of epidural anesthesia with muscle relaxants.
- There is a risk of damage to the anal sphincter from the insertion, extraction or repositioning of the rectal probe. To reduce this risk the probe would be inserted by a trained physician and with care, after pelvic muscle relaxation by epidural anesthesia.

Focal MR-Guided Focused Ultrasound Surgery of Intermediate risk, Localized Prostate Lesions

- There may be a risk of damage to the bladder from targeting a prostate area that is too close to the bladder. To mitigate this risk, the treating physician may utilize the system treatment tools as part of treatment planning to delineate the bladder area in question so that no “sonication” is allowed when they are close to the bladder. In any event, should a bladder injury event occur, cystoscopy may potentially be used to evaluate injury.
- Nerve damage, or loss of sensation in the area other than the treatment area.
- Risk of mechanical damage to the rectal wall by the insertion, extraction or repositioning of the transducer. To reduce this risk the probe would be inserted by a trained physician and with care.
- Hematuria – occurrence, duration and treatment will be recorded in the CRF and AE form
- Proteinuria – measurement will be by urine values; occurrence and duration will be recorded in the CRFs
- Hematospermia – occurrence, duration and treatment will be recorded in the CRF and AE form

7.1.7.1 *Other Treatment Related Risks*

- Deep Vein Thrombosis (DVT) - lying stationary for 3 to 4 hours, increases risk for DVT. The risk to the patient from lying still for this treatment should be no greater than that of lying still for any other reason. For treatments under this protocol, it will be the surgeon discretion to provide patients with compression stockings or wraps for the period of the treatment.
- Minor bruises redness and pain at the site of the intravenous catheter insertion – is common and usually subsides spontaneously within a few days.
- Phlebitis (local hardening of the vein) or infection from the intravenous catheter may occur in ~5% of the patients.

